ECG	Two copies of the ECG tracing should be obtained at the time of the ECG, one to be kept in the study file for retrospective collection by the sponsor if necessary. ECG data should be reviewed by personnel with experience in this study population			X			X	Week 36	Week 48 then every 12 weeks	X
Echocardiogram (ECHO)	Copies of all ECHOs and cardiology consultations performed on subjects who experience a >10% decrease in LVEF from baseline and whose cardiac ejection fraction is less than the institution's LLN will be collected for possible central review (ECHO to be performed by the same operator throughout the study, where possible, additional details are provided in the SPM). An ECHO does not need to be performed at study discontinuation unless one was not performed within the previous 8 weeks. French subjects please see Appendix 5 for echocardiogram schedule.		X	X	X		X	Week 36	Week 48 then every 12 weeks	X
Concomitant medications	See Protocol Section 8 for list of prohibited and cautionary medications.	X	X	X	X	X	X	Every 4 weeks	Every 4 weeks	X
Adverse events	Adverse event assessment should be continuous	X	X	X	X	X	X	Every 4 weeks	Every 4 weeks	X
Blood Sampling										
Chemistry	Evaluations performed by a local laboratory; Chemistry assessment should be performed at Week 36 for subjects with LCH for the LCH scoring assessment.	W4, W5, W6, W7	X	X	X	X	X	Week 32 then every 8 weeks; (also Week 36 for LCH only)	Week 48 then every 12 weeks	X
Hematology	Evaluations performed by a local laboratory	X	X	X	X	X	X	Week 32 then every 8 weeks	Week 48 then every 12 weeks	X

STUDY PHASE		TREATMENT WEEK 4+								Final Visit ²
		Week 4	Week 8	Week 12	Week 16	Week 20	Week 24	Weeks 28+	Weeks 48+	
Visit		±3	±3	±7	±7	±7	±7	±7	±7	
VISIT WINDOW (±days)		±3	±3	±7	±7	±7	±7	±7	±7	
Urinalysis		X	X	X	X	X	X	Week 32 then every 8 weeks	Week 48 then every 12 weeks	X
Spot urine protein/Cr ratio, spot urine albumin	Early morning specimen preferred	X	X	X	X	X	X	Week 32 then every 8 weeks	Week 48 then every 12 weeks	X
Clinical Activity and Biomarker Assessments										

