Target and non-target lesion assessment	Target and non-target lesions identified at time of screening scan must be re-assessed at each restaging scan. If the last radiographic assessment was more than 12 weeks prior to subject discontinuation from study and progressive disease has not been documented, a disease assessment should be obtained at the time of study discontinuation		X		X		X	Week 32 then every 8 weeks	Week 48 then every 12 weeks	X
Response for LGG, HGG, and other solid tumors	Target/non-target lesions: Complete response/partial response confirmation assessments may take place at Week 12 if initial response was seen at the Week 8 scan. Initial response (complete response/partial response) that is observed at Week 16 or after should be confirmed not less than 4 and not more than 8 weeks after the initial response.		X		X		X	Week 32 then every 8 weeks	Week 48 then every 12 weeks	X
Response for LCH	Response assessment for LCH include RECIST 1.1, LCH assessment, and LCH Scoring (Donadieu, 2004).			X			X	At week 36	Week 48 then every 12 weeks	X
Performance status (Karnofsky/Lansky)	See Appendix 3	X	X	X	X		X	Week 32 then every 8 weeks	Week 48 then every 12 weeks	X

STUDY PHASE		TREATMENT WEEK 4+							Final Visit ²
		Week 4	Week 8	Week 12	Week 16	Week 20	Week 24	Weeks 28+	
Visit									
VISIT WINDOW (\pm days)		± 3	± 3	± 7	± 7	± 7	± 7	± 7	± 7
Study Medication									
Dispense oral study medication and assess compliance	Dispense a 2 to 12 week supply of the study medication with instructions. Record dose reductions, dose interruptions/delays, and/or dose escalations.	X	X	X	X	X	X	Every 2-4 weeks	Every 4-12 weeks
Post Treatment Follow-up – See Section 9.4									
Dermatologic skin monitoring after IP discontinuation	Follow up dermatologic skin assessments should be performed every 2 to 3 months for 6 months following discontinuation of dabrafenib or until initiation of another anti-neoplastic therapy. (see Appendix 6 for French guidelines)								

1. MRI = magnetic resonance imaging; ECG = electrocardiogram; ECHO = echocardiogram.
2. Final study visit within 28 days after last dose of study drug.

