5.3.3.3 Efficacy Analyses

Anti-tumor activities will be calculated based on clinical evidence and the investigator-determined response assessment algorithms as described in [Appendix 2](#). Where appropriate, the lesion data will be listed for each subject. For subjects with solid tumors, the percent change from baseline and nadir will be calculated for each subject and listed, along with their calculated response [complete response (CR), partial response (PR), stable disease and progression of disease (PD)] according to response criteria in [Appendix 2](#). Response data will be summarized by disease cohort and by dose using the All Treated population. If the data warrant, the response data may also be summarized by the dose level of dabrafenib. For the LGG, HGG, and other solid tumors disease cohorts, response will also be assessed by an independent reviewer, and this data will be used to provide supportive analyses.

Additionally, all efficacy analyses will also be performed on the subset of central laboratory confirmed BRAF mutant subjects, excluding subjects who were centrally confirmed to be BRAF Wild-Type. In the event that central confirmation of mutation status is not obtained, the local laboratory testing result for BRAF mutation status will be utilized.

Response Rate (RR) with 95% exact confidence intervals will be calculated as the proportion of subjects with best overall response of confirmed CR or PR, as defined in [Appendix 2](#), relative to the total number of subjects treated in each expansion cohort. In the case of LCH subjects, the RR is the number of subjects assessed to have treatment response relative to the total number of subjects treated in that cohort. See [Appendix 2](#) for further information.

In addition to the frequentist analysis approach mentioned above, RR will be compared to the target RR using Bayesian posterior probabilities. A posterior estimate of RR will be calculated for each expansion cohort along with associated 95% credible intervals as calculated on

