- a. Progressive disease has not been documented and one or more target or non-target lesions have not been assessed.
- b. Change in method or technique for assessing target and non-target lesions as that used at baseline regardless of the justification of the change; e.g. if a participant develops a contraindication to MRI intravenous (IV) contrast media during the trial, a non-contrast MRI of the brain can be used (if possible); the participants response should only be recorded as not evaluable or progressive disease.

Definition of disease state, response criteria and response definition for LCH

Adapted from Histiocyte Society Evaluations and Treatment Guidelines, April 2009.

Definition of Disease State

NON ACTIVE DISEASE (NAD)	no evidence of disease	resolution of all signs or symptoms
ACTIVE DISEASE	regressive disease	regression of signs or symptoms, no new lesions*
	stable disease	persistence of signs of symptoms, no new lesions
	progressive disease	progression of signs or symptoms and/or appearance of new lesions**

*Plus partial or complete response by RECIST (Eisenhauer, 2009); and/or pulmonary criteria if applicable

** Isolated pulmonary LCH: improvement in lung function is >10% increase in baseline FEV1 or DLCO at time of disease assessment. Disease progression is >15% decline from baseline FEV1 or DLCO or FVC OR progression of symptoms (dyspnea, cough, constitutional symptoms) that cannot be explained by diagnoses other than pulmonary LCH (infection, heart disease, and/or other clinical issues excluded by careful clinical evaluation and testing)

** Isolated bone disease: progression is defined as appearance of new bone lesions or lesions in other organs

Response Criteria

BETTER	Complete Resolution	NAD
	Regression	AD Better
INTERMEDIATE	Mixed	New lesions in one site, regression in another site
	Stable	Unchanged
WORSE	Progression	

Response Definition for Efficacy

	3 Month Assessment	6 Month Assessment (performance relative to 3 month assessment)
Response	NAD or AD Better Mixed Stable	NAD or AD Better or Stable NAD or AD Better NAD or AD Better
Failure	NAD or AD Better NAD or AD Better Mixed or Stable ^a Progression	Mixed Progression Mixed or Stable ^a or Progression N/A

NAD = Non Active Disease

AD = Active Disease

Stable = Unchanged

Mixed = New lesions in one site, regression in another site

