^a Subjects who are assessed only as stable at the 3 and 6 month assessment are not considered a treatment response; however, they may be considered for continued treatment

LCH Scoring System (Donadieu, 2004)

Variable	Modality	Score
Bone (a)	Pain	1
	No Pain	0
Bone (b)	Compressing other organs (orbit or spine)	2
	No compression	0
Fever (>38.5°C)	Yes	1
	No	0
Lung: iconography	Pneumothorax	2
	Interstitial lesion on chest x-ray or lung CT	1
	Normal chest x-ray or lung CT	0
Lung: function	Mechanical ventilation or PFT >50%	5
	Supplemental oxygen or PFT between 50 and 80%	2
	No dysfunction, no cyanosis, no supplemental oxygen	0
Skin: area	25%	2
	5-25%	1
	Below 5%	0
Soft tissue tumor (including CNS)	5 cm maximum diameter	2
	2-5 cm maximum diameter	1

Variable	Modality	Score
	0-2 cm maximum diameter	0
Nodes (>2 cm)	Yes	1
	No	0
Liver	Below umbilicus	2
	Enlarged, above umbilicus	1
	Not enlarged	0
Spleen	Below umbilicus	2
	Enlarged, above umbilicus	1
	Not enlarged	0
Liver (enzymes)	>10 ULN	2
	3-10 ULN	1
	<3 ULN	0
Liver (gamma GT)	>10 ULN	2
	3-10 ULN	1
	<3 ULN	0
Albumin	Perfusion required in past week	3
	No perfusion but <30 g/L	1
	>30 g/L	0
Platelet: requirements in past week	More than two transfusions	4
	1 or 2 transfusions	3
	Low platelet count, no transfusion	2
	Normal count	0
Red cells: requirements in past week	More than 2 U	4
	1 or 2 U	3
	Hgb below 10 g/dL, no transfusion	1
	No transfusion	0

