2.5.2 Statistical hypothesis, model, and method of analysis

There are no formal tests of hypotheses planned for this trial. With respect to the primary objectives and endpoints, the primary focus will be on determining the maximum tolerated dose (or recommended dose based on available safety, PK, and response data), the safety profile, and PK/PD relationship of dabrafenib in pediatric patients with advanced BRAF V600-mutation positive solid tumors. Most analyses will be descriptive or exploratory.

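### In the LCH activity score, the 5-point lung-function row (PFT above 50%) conflicts with the 2- and 0-point rows, so unsupported patients can meet two rows or none

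*Protocol*

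**What the plan says.** Appendix 2 of the protocol (Section 15.2) ends with a 15-item LCH activity score. Its lung-function item has three rows:

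- 5 points: "Mechanical ventilation or PFT >50" per cent
- 2 points: "Supplemental oxygen or PFT between 50 and 80" per cent
- 0 points: "No dysfunction, no cyanosis, no supplemental oxygen"

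No text says which row applies when a patient meets two of them.

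The score is scheduled. Table 3-7 requires it at screening. Table 3-9 states: "Response assessment for LCH include RECIST 1.1, LCH assessment, and LCH Scoring", at Weeks 12, 24, 36 and 48 and every 12 weeks after that. Section 6.3 adds gamma GT for LCH patients so that the score can be completed, and Table 3-9 adds a blood draw: "Chemistry assessment should be performed at Week 36 for subjects with LCH for the LCH scoring assessment".

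The LCH response rate is defined elsewhere. Section 5.3.3.3 says: "In the case of LCH subjects, the RR is the number of subjects assessed to have treatment response", over the number treated. Appendix 2 defines that response by disease state (non-active, or active and better, mixed, stable or progressing) at 3 and 6 months. SAP Section 2.6.1 refers to Appendix 2 for the LCH criteria and plans response rates with 95% confidence intervals.

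**The concern.** A severity item should place each patient in one row and run in one direction. Here the 2-point row covers moderate impairment and the 0-point row covers none, so the 5-point row should cover the worst function. As printed, it covers function above 50%, which includes normal lungs. The score attached to mechanical ventilation then also fits a patient with nothing wrong, while a severely impaired patient breathing without support has no row.

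Lung function is the most heavily weighted item in the score. Two sites following the table in good faith could score the same patient differently, and one following it literally could rank a healthy lung above a badly damaged one for disease activity. Any listing or summary of the score would carry that error.

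**Working it through.** This is a check of a scoring table, so there is no power or error rate to reproduce. The SAP says (Section 2.5.2): "There are no formal tests of hypotheses planned for this trial".

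**Step 1: the rows as printed.** Inputs are the three rows above. Assumption: no dysfunction means PFT above 80% without oxygen or ventilation. Each cell gives the rows whose conditions are met.

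| PFT | No support | Oxygen | Ventilation |
|---|---|---|---|
| 30%, 45% | none | 2 | 5 |
| 50% | 2 | 2 | 5 and 2 |
| 65%, 80% | 5 and 2 | 5 and 2 | 5 and 2 |
| 90%, 100% | 5 and 0 | 5 and 2 | 5 |

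Without support, only a PFT of exactly 50% falls in a single row among the values tried.

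**Step 2: the same table with the 5-point row read as PFT below 50%.**

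| PFT | No support | Oxygen | Ventilation |
|---|---|---|---|
| 30%, 45% | 5 | 5 and 2 | 5 |
| 50%, 65%, 80% | 2 | 2 | 5 and 2 |
| 90%, 100% | 0 | 2 | 5 |

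Every unsupported patient now falls in exactly one row. The overlaps left come from the support terms joined by an or; scoring the highest applicable row settles them.

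**Step 3: other readings.**

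- *PFT as per cent loss.* A 60% loss meets both the 5- and 2-point rows, a 90% loss meets only the 5-point row, and a 30% loss meets none. This does not rescue the table.
- *Direction.* The pulmonary criteria in the same appendix say: "improvement in lung function is >10% increase in baseline FEV1 or DLCO at time of disease assessment". Higher is better in the protocol's own LCH criteria.
- *A fault in reading the PDF.* The Amendment 06 log in Appendix 7, which added this table, prints the same sign. Less-than signs elsewhere in the current table came through correctly. A one-off reading fault is unlikely.

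**Step 4: size.** The 15 item maxima, in table order, are 1 + 2 + 1 + 2 + 5 + 2 + 2 + 1 + 2 + 2 + 2 + 2 + 3 + 4 + 4 = 35.

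- Normal PFT, no support: 5 or 0, a difference of 5 points (5/35 = 14%).
- PFT above 50% up to 80%, no support: 5 or 2, a difference of 3 points.
- PFT below 50%, no support: no printed score, against 5 under the corrected row.
- PFT below 50% on oxygen: 2 as printed, against 5 under the corrected row and a highest-row rule, a difference of 3 points.

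**Step 5: Week 36 blood counts.** Table 3-9 adds Week 36 chemistry for LCH patients, but haematology runs at Week 32 and then every 8 weeks, so at Weeks 32 and 40. The platelet and red-cell items can reach 4 + 4 = 8 points, but their 3- and 4-point rows count transfusions or units given in the past week. Only the no-transfusion rows need a blood count: 2 for a low platelet count and 1 for low haemoglobin, so up to 3 points.

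**The case against.** The strongest reply is that the error may touch very little. Tables 3-7 and 3-9 schedule no pulmonary function test, so the item may usually have been scored from ventilation, oxygen or clinical status. Investigators may also have scored by evident intent, and nothing shows that they or the eCRF followed the printed sign. The Amendment 06 log says the score was added to establish baseline disease burden. Neither document shows an endpoint or summary built on it, and the earlier GSK SAP, to which the current SAP defers, is not available here. All of this stands. It limits the reach of the error without making the table right.

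Four stronger readings are tempting, and the documents do not support them:

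- *Normal lung function simply scores as severe.* It also meets the 0-point row, so it is classified twice. Likewise, PFT below 50% lacks a row only when the patient is on neither oxygen nor ventilation.
- *The change from baseline in disease activity is wrong.* No such analysis appears in either document.
- *The LCH response rate is biased.* It uses the disease-state definitions, whose pulmonary criteria have their own FEV1 and DLCO thresholds.
- *Eight of 35 points have no Week 36 value.* Transfusion history does not depend on a blood count, so at most 3 points do, and counts fall four weeks before and four weeks after.

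**Conclusion.** The lung-function item is wrong as printed. Its rows are neither exhaustive nor mutually exclusive, and the sign in the 5-point row runs against both adjacent rows and the protocol's own pulmonary criteria. A score that relies on a PFT value can be off by up to 5 of 35 points.

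How many scores are affected cannot be determined. Part 2 enrolled 11 LCH patients; SAP Section 2.1 pools Part 1 patients with them by disease, and the Part 1 LCH count is not given. Nor is the number of patients with lung involvement or a recorded PFT.

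The conclusion rests on the table's internal inconsistency and on reading no dysfunction as PFT above 80%. It does not rest on the cited scoring source, which was not consulted. The point deserves correction before the final report because the score is a scheduled part of LCH assessment, but it does not threaten the LCH response rate. The Week 36 haematology gap is a minor addition.

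**What to change.** 1. Check the 5-point row against the cited scoring source and correct it to PFT below 50%, the only direction that agrees with the 2- and 0-point rows.
2. State that the highest applicable row is scored when a patient meets more than one.
3. Ask sites how they scored the item, and re-derive scores where PFT values were recorded. Where none were, say so in the report.
4. State which haematology result feeds the Week 36 score when there has been no transfusion.

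The text change is one sign and two sentences. The re-derivation covers the 11 Part 2 patients plus any Part 1 LCH patients, and only visits with a recorded PFT. No new data collection is needed.

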15.3 Appendix 3: Performance Status Criteria / Scoring System

Karnofsky (age ≥ 16 years of age) and Lansky (age < 16 years) Performance Scores ([Yates, 1908](#))

PERFORMANCE STATUS CRITERIA			
Karnofsky and Lansky performance scores are intended to be multiples of 10			
Karnofsky		Lansky	
Score	Description	Score	Description
100	Normal, no complaints, no evidence of disease	100	Fully active, normal.
90	Able to carry on normal activity, minor signs or symptoms of disease.	90	Minor restrictions in physically strenuous activity.
80	Normal activity with effort; some signs or symptoms of disease.	80	Active, but tires more quickly
70	Cares for self, unable to carry on normal activity or do active work.	70	Both greater restriction of and less time spent in play activity.
60	Required occasional assistance, but is able to care for most of his/her needs.	60	Up and around, but minimal active play; keeps busy with quieter activities.
50	Requires considerable assistance and frequent medical care.	50	Gets dressed, but lies around much of the day; no active play, able to participate in all quiet play and activities.
40	Disabled, requires special care and assistance.	40	Mostly in bed; participates in quiet activities.
30	Severely disabled, hospitalization indicated. Death not imminent.	30	In bed; needs assistance even for quiet play.
20	Very sick, hospitalization indicated. Death not imminent.	20	Often sleeping; play entirely limited to very passive activities.
10	Moribund, fatal processes progressing rapidly.	10	No play, does not get out of bed.

The study will use the currently available dabrafenib capsule strengths (50 mg and 75 mg) from the adult program for children who are able to reliably swallow capsules. In addition, two lower strength capsules (10 mg and 25 mg) and an oral suspension formulation are available for pediatric subjects who may have difficulty swallowing larger capsules. The suspension will only be available at those sites that are capable of and meet the applicable regulatory requirements to prepare the suspension.

Revised Text:

The study will use the currently available dabrafenib capsule strengths (50 mg and 75 mg) from the adult program for children who are able to reliably swallow capsules. In addition, two lower strength capsules (10 mg and 25 mg) and an oral suspension formulation are available for pediatric subjects who may have difficulty swallowing larger capsules. The suspension will only be available at those sites that are capable of and meet the applicable regulatory requirements to prepare the suspension. **In France, children younger than 6 years and children older than 6 years with a risk of choking when swallowing capsules cannot be included in the study, pending availability of an oral suspension formulation.**

Change #2, Section 3.6, Investigational Product and Other Study Treatment Dosage/Administration; rationale for change: in response to ANSM review of the protocol.

Previous Text

Capsules: Dabrafenib capsules will be supplied by GSK (for subjects able to reliably and consistently swallow capsules).

Suspension: Bottles of bulk GSK2118436B drug substance with bottles of individual excipients (4 components) will be supplied by GSK for on-site extemporaneous compounding of a suspension formulation (for subjects unable to swallow capsules). Only sites meeting local, applicable regulations regarding extemporaneous compounding will be permitted to enroll subjects requiring suspension administration. Detailed preparation instructions are supplied in the SPM. The suspension will be administered with an oral dosing syringe supplied by GSK (oral syringes, 1 mL, 5 mL, and 20 mL for single use).

Revised Text (added to beginning of section):

In France: Children younger than 6 years and children older than 6 years with a risk of choking when swallowing capsules cannot be included in the study, pending availability of an oral suspension formulation.

Capsules: Dabrafenib capsules will be supplied by GSK (for subjects able to reliably and consistently swallow capsules).

Suspension: Bottles of bulk GSK2118436B drug substance with bottles of individual excipients (4 components) will be supplied by GSK for on-site extemporaneous compounding of a suspension formulation (for subjects unable to swallow capsules). Only sites meeting local, applicable regulations regarding extemporaneous compounding will be permitted to enroll subjects requiring suspension administration. Detailed preparation instructions are supplied in the SPM. The suspension will be administered with an oral dosing syringe supplied by GSK (oral syringes, 1 mL, 5 mL, and 20 mL for single use).

Change #3, Section 3.7.8, QTc Stopping Criteria; rationale for change: in response to ANSM review of the protocol.

Previous Text:

A subject that meets the criteria below will be withdrawn from the study. The QT correction formula used to determine discontinuation should be the same one used throughout the study [QT duration corrected for heart rate by Bazett's formula (QTcB)].

- QTcB >500 msec or uncorrected QT >600 msec
- If subject has underlying bundle branch block then the QTcB withdrawal criteria depends on the baseline value:

Baseline QTcB value (with underlying bundle branch block)	QTcB withdrawal criteria
<450 ms	>500 ms
450-480 ms	≥530 ms

Withdrawal decisions are to be based on an average QTcB value of triplicate ECGs. If an ECG demonstrates a prolonged QT interval, obtain 2 more ECGs over a brief period (e.g., 5 minutes between each ECG), and then use the averaged QTcB values of the 3 ECGs to determine whether the subject should be discontinued from the study.

Revised Text:

Withholding and Stopping Criteria for QTc Prolongation for Subjects Enrolled in France

QTc-Prolongation¹ Action and Dose Modification

QTc-Prolongation ¹	Action and Dose Modification
QTcB \geq 501 msec	Interrupt study treatment until QTcB prolongation resolves to grade 1 or baseline
	Restart at current dose level ²
	If event recurs, permanently discontinue study treatment

1. Abbreviations: msec = milliseconds; QTcB = QT interval on electrocardiogram corrected using the Bazett's formula1. Based on average QTc value of triplicate ECGs. For example, if an ECG demonstrates a prolonged QT interval, obtain two or more ECGs over a brief period, and then use the averaged QTc values of the three ECGs to determine if study treatments should be interrupted or discontinued.2. If the QTc prolongation resolves to grade 1 or baseline, the subject may resume study treatment if the investigator and GSK medical monitor agree that the subject will benefit from further treatment.	

Change #4, Section 3.8, Time and Events Schedule (Table 10); rationale for change: add ECHO at Week 4 in response to ANSM review of the protocol.

Previous Table:

Table 10 Part 1 and Part 2 Treatment Phase: Week 4 through End of Study

STUDY PHASE		TREATMENT WEEK 4+								Final Visit
		Week 4	Week 8	Week 12	Week 16	Week 20	Week 24	Weeks 25-56	Weeks 57+	
Visit		±3	±3	±7	±7	±7	±7	±7	±7	
VISIT WINDOW (±days)		±3	±3	±7	±7	±7	±7	±7	±7	
Safety Assessments										
Brief Physical examination	Will include height and weight, and assessments of the skin, lungs, cardiovascular system, and abdomen (liver and spleen) [and neurological exam as clinically indicated]	X	X	X		X		Every 8 weeks	Every 12 weeks	X
Urine Pregnancy test	For menstruating females and as required per local applicable regulations	X	X	X	X	X	X	Every 4 weeks	Every 4 weeks	X
Vital signs	Blood pressure, body temperature, pulse rate, respirations	X	X	X	X	X	X	Every 4 weeks	Every 4 weeks	X
Dermatologic skin assessment	Performed by the investigator (or dermatologist, at the discretion of the investigator). If possible, the same physician should perform each exam for the duration of the study to ensure consistency between evaluations. Photographs of suspect lesions at baseline are recommended with photographs and/or biopsies of any new or changing lesions recommended at subsequent on-study visits.		X		X			Every 12 weeks	Every 12 weeks	X
ECG	Two copies of the ECG tracing should be obtained at the time of the ECG, one to be kept in the study file for retrospective collection by the sponsor if necessary. ECG data should be reviewed by personnel with experience in this study population			X			X	Every 12 weeks	Every 12 weeks	X

STUDY PHASE		TREATMENT WEEK 4+								Final Visit
		Week 4	Week 8	Week 12	Week 16	Week 20	Week 24	Weeks 25-56	Weeks 57+	
Visit		±3	±3	±7	±7	±7	±7	±7	±7	
VISIT WINDOW (±days)		±3	±3	±7	±7	±7	±7	±7	±7	
Echocardiogram (ECHO)	Copies of all ECHOs and cardiology consultations performed on subjects who experience a >10% decrease in LVEF from baseline and whose cardiac ejection fraction is less than the institution's LLN will be collected for possible central review (additional details are provided in the SPM). An ECHO does not need to be performed at study discontinuation unless one was not performed within the previous 8 weeks.		X	X	X		X	Every 8 weeks	Every 8 weeks	X
Concomitant medications	See Protocol Section 8 for list of prohibited and cautionary medications.	X	X	X	X	X	X	Every 4 weeks	Every 4 weeks	X
Adverse events	Adverse event assessment should be continuous	X	X	X	X	X	X	X	X	X
Blood Sampling										
Chemistry	Evaluations performed by a local laboratory	X	X	X	X	X	X	Every 8 weeks	Every 8 weeks	X
Hematology	Evaluations performed by a local laboratory	X	X	X	X	X	X	Every 8 weeks	Every 8 weeks	X
Clinical Activity Assessments										
Target and non-target lesion assessment	Target and non-target lesions identified at time of screening scan must be re-assessed at each restaging scan. If the last radiographic assessment was more than 12 weeks prior to subject discontinuation from study and progressive disease has not been documented, a disease assessment should be obtained at the time of study discontinuation		X		X		X	Every 8 weeks	Every 12 weeks (or as per standard of care)	X

STUDY PHASE		TREATMENT WEEK 4+								Final Visit
		Week 4	Week 8	Week 12	Week 16	Week 20	Week 24	Weeks 25-56	Weeks 57+	
Visit		±3	±3	±7	±7	±7	±7	±7	±7	
VISIT WINDOW (±days)										
Response	Complete response/partial response confirmation assessments may take place at Week 12 if initial response was seen at the Week 8 scan. Initial response (complete response/partial response) that is observed at Week 16 or after should be confirmed not less than 4 and not more than 8 weeks after the initial response.		X		X		X	Every 8 weeks	Every 12 weeks	X
Performance status (Karnofsky/Lansky)	See Appendix 3	X	X	X	X		X	Every 8 weeks	Every 12 weeks	X
Study Medication										
Dispense oral study medication and assess compliance	Dispense a 2 to 4 week supply of the study medication with instructions. Record dose reductions, dose interruptions/delays, and/or dose escalations.	X	X	X	X	X	X	Every 2-4 weeks	Every 2-4 weeks	
Post Treatment Follow-up – See Section 9.4										

1. MRI = magnetic resonance imaging; ECG = electrocardiogram; ECHO = echocardiogram

Revised Table:

Table 10 Part 1 and Part 2 Treatment Phase: Week 4 through End of Study

STUDY PHASE		TREATMENT WEEK 4+								Final Visit
		Week 4	Week 8	Week 12	Week 16	Week 20	Week 24	Weeks 25-56	Weeks 57+	
Visit		±3	±3	±7	±7	±7	±7	±7	±7	
VISIT WINDOW (±days)		±3	±3	±7	±7	±7	±7	±7	±7	
Safety Assessments										
Brief Physical examination	Will include height and weight, and assessments of the skin, lungs, cardiovascular system, and abdomen (liver and spleen) [and neurological exam as clinically indicated]	X	X	X		X		Every 8 weeks	Every 12 weeks	X
Urine Pregnancy test	For menstruating females and as required per local applicable regulations	X	X	X	X	X	X	Every 4 weeks	Every 4 weeks	X
Vital signs	Blood pressure, body temperature, pulse rate, respirations	X	X	X	X	X	X	Every 4 weeks	Every 4 weeks	X
Dermatologic skin assessment	Performed by the investigator (or dermatologist, at the discretion of the investigator). If possible, the same physician should perform each exam for the duration of the study to ensure consistency between evaluations. Photographs of suspect lesions at baseline are recommended with photographs and/or biopsies of any new or changing lesions recommended at subsequent on-study visits.		X		X			Every 12 weeks	Every 12 weeks	X
ECG	Two copies of the ECG tracing should be obtained at the time of the ECG, one to be kept in the study file for retrospective collection by the sponsor if necessary. ECG data should be reviewed by personnel with experience in this study population			X			X	Every 12 weeks	Every 12 weeks	X

STUDY PHASE		TREATMENT WEEK 4+							Final Visit	
		Week 4	Week 8	Week 12	Week 16	Week 20	Week 24	Weeks 25-56		Weeks 57+
Visit		±3	±3	±7	±7	±7	±7	±7	±7	
VISIT WINDOW (±days)		±3	±3	±7	±7	±7	±7	±7	±7	
Echocardiogram (ECHO)	Copies of all ECHOs and cardiology consultations performed on subjects who experience a >10% decrease in LVEF from baseline and whose cardiac ejection fraction is less than the institution's LLN will be collected for possible central review (ECHO to be performed by the same operator throughout the study, where possible; additional details are provided in the SPM). An ECHO does not need to be performed at study discontinuation unless one was not performed within the previous 8 weeks.	X	X	X	X		X	Every 8 weeks	Every 8 weeks	X
Concomitant medications	See Protocol Section 8 for list of prohibited and cautionary medications.	X	X	X	X	X	X	Every 4 weeks	Every 4 weeks	X
Adverse events	Adverse event assessment should be continuous	X	X	X	X	X	X	X	X	X
Blood Sampling										
Chemistry	Evaluations performed by a local laboratory	X	X	X	X	X	X	Every 8 weeks	Every 8 weeks	X
Hematology	Evaluations performed by a local laboratory	X	X	X	X	X	X	Every 8 weeks	Every 8 weeks	X
Clinical Activity Assessments										
Target and non-target lesion assessment	Target and non-target lesions identified at time of screening scan must be re-assessed at each restaging scan. If the last radiographic assessment was more than 12 weeks prior to subject discontinuation from study and progressive disease has not been documented, a disease assessment should be obtained at the time of study discontinuation		X		X		X	Every 8 weeks	Every 12 weeks (or as per standard of care)	X

STUDY PHASE		TREATMENT WEEK 4+								Final Visit
		Week 4	Week 8	Week 12	Week 16	Week 20	Week 24	Weeks 25-56	Weeks 57+	
Visit		±3	±3	±7	±7	±7	±7	±7	±7	
VISIT WINDOW (±days)										
Response	Complete response/partial response confirmation assessments may take place at Week 12 if initial response was seen at the Week 8 scan. Initial response (complete response/partial response) that is observed at Week 16 or after should be confirmed not less than 4 and not more than 8 weeks after the initial response.		X		X		X	Every 8 weeks	Every 12 weeks	X
Performance status (Karnofsky/Lansky)	See Appendix 3	X	X	X	X		X	Every 8 weeks	Every 12 weeks	X
Study Medication										
Dispense oral study medication and assess compliance	Dispense a 2 to 4 week supply of the study medication with instructions. Record dose reductions, dose interruptions/delays, and/or dose escalations.	X	X	X	X	X	X	Every 2-4 weeks	Every 2-4 weeks	
Post Treatment Follow-up – See Section 9.4										

1. MRI = magnetic resonance imaging; ECG = electrocardiogram; ECHO = echocardiogram

15.6 Appendix 6 French Country Guidelines for additional dermatological monitoring while on therapy and after IP discontinuation

This Section applies to subject enrolled in France **only**.

Cutaneous Squamous Cell Carcinoma (cuSCC) and New primary melanoma

Dermatological examinations should be performed prior to initiation of study treatment, monthly during treatment, and monthly for 6 months following discontinuation of dabrafenib or until initiation of another anti-neoplastic therapy, whichever comes first. Subjects should be instructed to immediately inform their physician if new lesions develop. Any cuSCC or new primary melanoma should be reported as a protocol-specific SAE and treated according to standard clinical practice.

Non-cutaneous secondary/recurrent malignancy

Prior to initiation of study treatment subjects should undergo a head and neck examination with minimally visual inspection of oral mucosa and lymph node palpation, as well as chest/abdomen Computed Tomography (CT) scan. During treatment subjects should be monitored as clinically appropriate which may include a head and neck examination every 3 months and a chest/abdomen CT scan every 6 months. Anal examinations and pelvic examinations are recommended before the start of and at the end of treatment or when considered clinically indicated. Complete blood cell counts should be performed as clinically indicated. Following discontinuation of dabrafenib monitoring for non-cutaneous secondary/recurrent malignancies should continue for up to 6 months or until initiation of another anti-neoplastic therapy, whichever comes first. Any non-cutaneous secondary/recurrent malignancy should be reported as a protocol-specific SAE and treated according to standard clinical practice.

